Study Document Cover Page

Official Title: Brain Dynamic Audio Stimulation for Improving Sleep Quality and Circadian Rhythm in Healthcare Workers

Short Title: Brain Dynamic Audio Stimulation

Document Type: Study Protocol

IRB Number: CMMC IRB No. 11404-012

Organization Name: Chi Mei Medical Center (CMMC)

Principal Investigator: [name]

Document Date: 2025-10-21

Version: 1.0

Confidentiality Statement: This document contains confidential information intended for regulatory and research purposes only.

Study Protocol

Title:

Effectiveness of Brain Dynamic Audio Stimulation for Improving Insomnia and Sleep Cycles in Healthcare Professionals (BDAS-HP)

Protocol ID: 11404-012

Institution: Chi Mei Medical Center, Tainan, Taiwan

Principal Investigator: [name]

IRB Number: CMMC IRB No. 11404-012

Approval Date: May 6, 2025

Document Date: January 1, 2026

Version: 2.0

1. Background and Rationale

Healthcare professionals are at high risk of insomnia and impaired sleep quality due to shift work, occupational stress, and high cognitive demands. Poor sleep is associated with decreased attention, emotional dysregulation, burnout, and increased medical errors.

Brain Dynamic Audio Stimulation (BDAS) is a non-invasive auditory intervention that delivers frequency-specific sound patterns designed to entrain neural oscillations toward brainwave frequencies associated with relaxation and sleep, particularly theta (θ) and delta (δ) bands. This mechanism is hypothesized to facilitate sleep initiation and improve sleep stability.

The present study aims to evaluate the clinical feasibility and preliminary effectiveness of BDAS using both subjective outcomes (Insomnia Severity Index, ISI) and objective sleep-related parameters derived from short-duration polysomnographic EEG recordings, sleep onset latency, and sleep efficiency.

2. Objectives

Primary Objective:

To evaluate changes in insomnia severity, measured by the **Insomnia Severity Index (ISI)**, before and after BDAS intervention.

Secondary Objective:

To assess changes in:

- Sleep onset success rate
- Sleep onset latency

- Sleep efficiency following BDAS exposure

To explore short-term changes in **sleep stage distribution** using EEG-based sleep hypnograms.

3. Study Design

This is a **prospective, single-group, pretest-posttest interventional study**.

Fifteen healthcare professionals aged 20–65 years with subjective sleep disturbances will be recruited. Participants will undergo a **30-minute BDAS session daily for two consecutive weeks** in a controlled environment at Chi Mei Medical Center.

Pre- and post-intervention assessments include ISI and quantitative EEG recordings.

4. Participants

Inclusion Criteria

- Licensed healthcare workers at Chi Mei Medical Center (nurses, physicians, therapists, social workers).
- Age 20–65 years.
- Subjective sleep disturbance for at least one month.
- Willing and able to participate for two weeks.
- Provided written informed consent.

Exclusion Criteria

- Current use of hypnotics, antidepressants, or psychiatric medications.
- Diagnosed sleep disorders (e.g., OSA, narcolepsy).
- Neurological or psychiatric illness, epilepsy, or severe chronic disease.
- Hearing impairment affecting audio perception.
- Pregnancy or breastfeeding.

5. Intervention: Brain Dynamic Audio Stimulation (BDAS)

Participants will receive **30 minutes of BDAS** each night for 14 days.

The audio files consist of sound frequencies designed to entrain brainwave patterns associated with deep relaxation (delta, theta) and restorative sleep.

Sessions will take place in a quiet, dimly lit room under standardized conditions. No pharmacological agents will be administered.

6. Outcome Measures

Primary Outcome:

Subjective Outcome

- Insomnia Severity Index (ISI)
 - Baseline (pre-intervention)
 - Post-intervention (after 2 weeks of BDAS use)

Objective Outcomes

- EEG-derived sleep hypnogram based on AASM criteria
- Sleep onset success rate
- Sleep onset latency (seconds)
- Sleep efficiency (sleep time / total recording time)

EEG, EOG, and EMG signals are used to infer sleep stages (Wake, N1, N2, N3, REM).

7. Statistical Analysis

ISI Score Analysis

- **Paired-sample t-tests** to compare pre- and post-intervention ISI scores
- Effect sizes calculated using **Cohen's d** and **Hedges' g**

Sleep Onset Latency Analysis

- Independent-sample t-tests are used to compare latency before and after two weeks of use
- Each sleep session is treated as an independent observation to maximize statistical power

Sleep Efficiency Analysis

- Independent-sample t-tests comparing pre-intervention and post-intervention sleep efficiency
- Effect sizes reported using Cohen's d and Hedges' g

Statistical Significance

- Two-tailed tests
- $p < 0.05$ considered statistically significant

8. Ethical Considerations

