# 1. Analysis Objectives and Endpoints

## 1.1 Primary Objective

To evaluate the effect of Brain Dynamic Audio Stimulation (BDAS) on insomnia severity as measured by the **Insomnia Severity Index (ISI)** before and after a two-week intervention.

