## 1.2 Secondary Objectives

To assess the effect of BDAS on objective sleep-related parameters, including:

- Sleep onset success rate
- Sleep onset latency
- Sleep efficiency
- Short-term sleep stage distribution derived from EEG-based hypnograms

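### Does Protocol 6 turn the EEG sleep outcomes into primary outcomes alongside ISI?

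*Protocol*

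**What the plan says.** Protocol 6 opens with "Primary Outcome". Beneath it stand a subjective block, with ISI at baseline and after two weeks, and then "Objective Outcomes", which lists the EEG-derived hypnogram, onset success rate, onset latency and efficiency. No further rank label appears before Protocol 7.

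Protocol 2 does separate the ranks. ISI is the primary objective. Onset success, latency and efficiency come under "Secondary Objective", followed by a sentence on sleep stages that begins "To explore short-term changes in".

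The SAP ranks outcomes three times. SAP 1.1 gives the primary objective as "To evaluate the effect of Brain Dynamic Audio Stimulation (BDAS) on insomnia severity as measured by the" ISI. SAP 1.2 lists the objective sleep parameters as secondary, including "Short-term sleep stage distribution derived from EEG-based hypnograms". SAP 1.3 names the mean change in total ISI score as the one primary endpoint and puts all the EEG measures among the secondary endpoints. The titles of SAP 5.1 to 5.5 run primary (ISI), secondary (onset success, latency, efficiency) and exploratory (sleep stages).

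**The concern.** The outcomes section is where a reader first looks for the rank of an endpoint, and in Protocol 6 nothing marks where the primary list ends. Latency and efficiency each have a planned test at an unadjusted two-sided 5% level (Protocol 7; SAP 3, 5.3 and 5.4), and neither document says how several tests are to be handled. If ISI showed no change, someone relying on Protocol 6 alone could present a significant latency or efficiency result as a primary finding. Protocol 2 and SAP 1.3 would not allow that.

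The exposure is limited to those two outcomes. Onset success has no inferential test (SAP 5.2). Sleep-stage tests are applied only where appropriate, and their results are read descriptively (SAP 5.5).

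**Working it through.** The question is mainly textual, so the ranks are set side by side.

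| Place | ISI | Onset success | Latency | Efficiency | Sleep stages |
|---|---|---|---|---|---|
| Protocol 2 | primary | secondary | secondary | secondary | under the secondary objective, worded as exploring |
| Protocol 6 | directly under the primary heading | no label of its own | no label of its own | no label of its own | no label of its own |
| SAP 1.1, 1.2 | primary | secondary | secondary | secondary | secondary |
| SAP 1.3 | primary | secondary | secondary | secondary | secondary |
| SAP 5.1 to 5.5 | primary | secondary, no test | secondary | secondary | exploratory |

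Three points follow.

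1. For ISI, onset success, latency and efficiency, every row that assigns a rank agrees. Protocol 6 disagrees only if its first heading governs both blocks. That heading is singular and sits immediately above the ISI block, while the EEG block has its own plural heading. The text available for review does not preserve heading levels, so the scope cannot be settled from layout.

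2. Sleep stages vary in rank within the SAP itself (1.2 and 1.3 against 5.5). Layout does not explain this, but nothing turns on it, because SAP 5.5 fixes how the results are read.

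3. The sample size supports the same hierarchy. SAP 7 uses an ISI reduction of about 5 points with SD about 4, and makes no formal calculation for secondary outcomes. It states no power figure to reproduce. With N = 15, a paired t-test and two-sided 5%:
   - SD 4 taken as the SD of change: d = 5/4 = 1.25, noncentrality 1.25 × √15 = 4.84 on 14 degrees of freedom, power 99.4%.
   - SD 4 taken as the SD of scores, assumed pre-post correlation 0: SD of change = 4 × √2 = 5.66, d = 5/5.66 = 0.88, power 88.9%.

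   The study is adequately sized for ISI as sole primary on either reading of the SD.

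**Size of the literal reading.** Suppose the three outcomes tested in Protocol 7 (ISI, latency, efficiency) were all primary, each at a true 5% level:
   - independent tests: 1 − 0.95³ = 1 − 0.857 = 14.3%;
   - upper bound for any dependence: 3 × 5% = 15%;
   - latency and efficiency tests correlated, since both come from the same recordings and time awake before sleep onset lowers efficiency: about 13.6% at an assumed absolute correlation of 0.5 and 11.7% at 0.9, with ISI independent;
   - ISI alone: 5%.

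These figures describe a hierarchy that SAP 1.3 rules out.

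**The case for a change.** The strongest case for a change is that Protocol 6 is the defining section for outcomes and that neither document says which prevails. Loss of layout would more readily blur heading levels than delete a secondary label, and Protocol 2 kept both of its rank labels. Added headings and one sentence on unadjusted p-values would cost almost nothing and would remove a choice that could otherwise be made after seeing results.

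What stands is that Protocol 6 lacks a label and that sleep stages have two ranks. What does not stand is the consequence. Promoting latency or efficiency would contradict the endpoint list in SAP 1.3 and the titles of SAP 5.3 and 5.4. SAP 10 requires departures from the SAP to be documented with justification and described in publications.

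It could also be argued that the real error rates are worse than 5% per test, because for latency the plan says "Each sleep session is treated as an independent observation to maximize statistical power". That is a fair criticism of the analysis method in Protocol 7 and SAP 5.3, but a separate one. Relabelling the outcomes leaves every planned test as it is, so those tests would have the same error rates before and after. They do not measure what is at stake in a heading.

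**Conclusion.** The concern does not call for a change. Protocol 6 has a clerical slip, a missing or ambiguous rank label, and the SAP ranks sleep stages in two ways. The intended hierarchy is plain from Protocol 2, SAP 1.1 to 1.3, the section titles of SAP 5 and the basis of the sample size: ISI change is the sole primary, and latency and efficiency are secondary.

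An analyst following the SAP tests ISI as the single primary at 5%. The 14.3% figure applies only if Protocol 6 is read alone and against the SAP, with three independent tests that each hold 5%. Relabelling would alter no test, estimate, sample size or conclusion. This rests on the SAP governing the analysis and on its deviation rule being followed. In a study that SAP 7 calls exploratory, with 15 participants, an added multiplicity procedure would bring no gain.

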## 1.3 Endpoints

### Primary Endpoint

- Mean change in total ISI score from baseline (pre-intervention) to post-intervention (after 2 weeks)

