## 2. Analysis Populations

Population	Definition
Full Analysis Set (FAS)	All participants who received at least one BDAS session and provided baseline ISI data
Per-Protocol Set (PPS)	Participants completing $\geq 80\%$ of BDAS sessions without major protocol deviations
Safety Set	All participants who initiated BDAS intervention

- Primary analyses will be conducted on the **FAS**
- Sensitivity analyses will be performed using the **PPS**

---

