## 4. Handling of Missing Data

- For ISI analysis, participants with both baseline and post-intervention data will be included
- No imputation will be performed for missing objective sleep measures
- Sensitivity analyses excluding incomplete cases will be conducted to assess robustness

---

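### The protocol ties the only post-baseline ISI to two weeks of BDAS use, so participants who stop early may have no second score and drop out of the primary analysis

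*Protocol*

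**What the plan says.** Protocol 6 (Outcome Measures) lists two ISI assessments, one at baseline and one described as "Post-intervention (after 2 weeks of BDAS use"). The timing of the second refers to use of the intervention.

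SAP 1.3 defines the primary endpoint as "Mean change in total ISI score from baseline (pre-intervention) to post-intervention (after 2 weeks"). Here the two weeks carry no condition on use.

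SAP 2 defines the FAS as "All participants who received at least one BDAS session and provided baseline ISI data", and adds that "Primary analyses will be conducted on the FAS". A second ISI is not needed to belong to the FAS.

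SAP 4 states: "For ISI analysis, participants with both baseline and post-intervention data will be included". It gives no imputation or model for a missing ISI. It also announces "Sensitivity analyses excluding incomplete cases will be conducted to assess robustness".

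The available text has no ISI at early termination, and no statement on whether the ISI is sought from someone who has stopped BDAS.

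**The concern.** Consider a participant who gives up on day 4. SAP 2 places that person in the primary population. On the protocol wording the person never reaches the second assessment, and SAP 4 then removes them. The primary result would be labelled FAS but would lack some people whom the FAS definition covers.

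This matters because the study has one group and the mean ISI change is the whole primary result. There is no control arm in which similar losses might offset the effect. The course is 14 daily on-site sessions for staff whom Protocol 1 describes as affected by shift work and occupational stress, so some stopping is plausible. Lack of perceived benefit is one plausible reason for it. If so, the missing scores would tend to be the less favourable ones. Clinical feasibility is also a stated aim in Protocol 1, so what happens to those who stop is of interest in itself.

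A score that was never collected cannot be recovered in the analysis. The remedy therefore belongs in the assessment schedule.

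**Working it through.** **1. The plan's own figure.** SAP 7 gives a mean reduction of about 5 points, an SD of about 4 and 15 participants, and calls the power sufficient without a number. Taking 4 as the SD of the change (the SAP does not say), d = 5/4 = 1.25. A two-sided paired t-test at 0.05 with n = 15 (noncentral t, 14 degrees of freedom, noncentrality 1.25 × √15) has 99.4% power. The claim is reproduced. With 12 participants analysed the power is still 97.6%, and with 10 it is 93.9%. On these inputs, losing stoppers is a matter of bias and not of power.

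**2. Following an early stopper through the text.**

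| Place | Consequence for the stopper |
|---|---|
| SAP 2 | In the FAS (one session and a baseline ISI) |
| Protocol 6 | No second ISI scheduled, if timing depends on use |
| SAP 1.3 | Second ISI possible, if two weeks means calendar time |
| SAP 4, main ISI analysis | Dropped if the second ISI is absent |
| SAP 4, sensitivity analysis | Also excludes incomplete cases, as the main ISI analysis already does |
| SAP 8, sensitivity analyses | Outlier exclusion, non-parametric tests and the Per-Protocol Set (PPS): none restores the person |

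**3. Size of the effect if stoppers are lost.** The number of stoppers k and their mean improvement m are assumptions, because the documents give neither. The improvement of 5 points in those who stay is the SAP 7 figure, and 15 is the planned sample size.

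Mean over all treated = [(15 − k) × 5 + k × m] / 15

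Overstatement = 5 − that mean = k × (5 − m) / 15

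| k | m = 0: mean, overstatement | m = 2.5: mean, overstatement | m = 5: mean, overstatement |
|---|---|---|---|
| 1 | 4.67, 0.33 | 4.83, 0.17 | 5.00, 0 |
| 2 | 4.33, 0.67 | 4.67, 0.33 | 5.00, 0 |
| 3 | 4.00, 1.00 | 4.50, 0.50 | 5.00, 0 |
| 4 | 3.67, 1.33 | 4.33, 0.67 | 5.00, 0 |

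For example, with k = 3 and m = 0 the mean is (12 × 5 + 3 × 0)/15 = 4.00, an overstatement of 1.00. With k = 0 there is none.

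**4. Do the FAS and PPS still differ?** The PPS requires at least 80% of sessions: 0.80 × 14 = 11.2, so 12 of 14 (11/14 = 78.6% falls short). Someone who attends 11 or fewer sessions but stays to the end can give a second ISI. That person is in the FAS analysis and outside the PPS.

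**The case against.** The strongest objection is that the plan is silent here, not exclusionary. The protocol phrase may simply name the end of a fixed 14-day course. The SAP endpoint can be read as calendar time, nothing forbids asking a stopper for an ISI at two weeks, and SAP 4 would then include it. This stands: a reader might infer that the schedule explicitly excludes stoppers, and the documents do not say so. What remains is that the two documents can be read differently on whether a stopper is measured, and the protocol reading loses the score.

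A reader might also infer that the FAS analysis shrinks to those who stayed on BDAS, so that the FAS and PPS have little to contrast. The documents do not support this either. Participants with low attendance or a major deviation can still supply a second ISI, and they separate the two sets.

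The size is also open to challenge. Zero improvement among stoppers is an extreme choice in an uncontrolled before-and-after study. Shift schedules may cause stopping that has nothing to do with benefit, and inclusion requires willingness to take part for two weeks. These points are fair, and they are why a range down to zero is shown.

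Finally, parts of the documents were not available, including the body of Protocol 8 (Ethical Considerations). A withdrawal rule there cannot be ruled out.

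**Conclusion.** The point holds as an ambiguity in timing with a possible bias attached. Read by the protocol wording, early stoppers have no scheduled second ISI, SAP 4 removes them from a primary analysis that SAP 2 says includes them, and no planned analysis brings them back.

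Whether this biases the result depends on two unknowns: how many stop, and how they fare. With one to four stoppers among 15, the overstatement runs from nothing, through 0.17 to 0.67 points at an improvement of 2.5, to 0.33 to 1.33 points at an improvement of 0. The formula also shows that the direction would reverse if stoppers improved by more than 5 points. The upper values illustrate an unfavourable case and are not a forecast.

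The study is exploratory and its power on the SAP's inputs is hardly affected. The change is still worth making before data collection ends, because it is cheap and the missing scores cannot be reconstructed later.

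**What to change.** Use the same calendar-based timing in Protocol 6 and SAP 1.3, for example:

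> The post-intervention ISI is collected two weeks after the first BDAS session, within a short prespecified window, from every participant who received at least one session, whether or not BDAS was continued.

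Allow remote completion for those who no longer attend, and record the mode. State in SAP 2 and SAP 4 that these scores enter the FAS analysis, and keep the PPS as the on-treatment analysis. This alters data collection only.

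The cost is a sentence or so in each document and one short questionnaire per early stopper. There are two downsides: remote completion may introduce a small mode difference between stoppers and those who attend, and the reported mean change may be somewhat smaller.

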### 5.2 Secondary Analysis: Sleep Onset Success Rate

- Sleep onset success will be defined as transition from wakefulness to any sleep stage during the recording period
- Success rates will be summarized descriptively as proportions (%)
- No inferential testing is planned due to the exploratory nature of this endpoint

---

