### 5.3 Secondary Analysis: Sleep Onset Latency

- Sleep onset latency is defined as time (seconds) from recording start to first epoch of sleep
- **Independent-sample t-tests** will be used to compare latency between:
  - Initial use
  - After 2 weeks of BDAS use
- Each sleep session will be treated as an **independent observation** to maximize statistical power
- Effect sizes will be reported using Cohen's d and Hedges' g

---

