### 5.4 Secondary Analysis: Sleep Efficiency

- Sleep efficiency is defined as: **(Total sleep time / total recording time) × 100%**
- Independent-sample t-tests will be used to compare sleep efficiency before and after BDAS intervention
- Effect sizes (Cohen's d, Hedges' g) and 95% CIs will be reported

---

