## 9. Reporting of Results

- Results will be reported as:
  - Mean  $\pm$  SD
  - Mean difference (95% CI)
  - p-values and effect sizes
- Graphical presentations may include:
  - ISI pre-post boxplots
  - Sleep onset latency distributions
  - Sleep efficiency comparison plots
  - Sleep hypnogram examples

---

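### Sleep onset latency and sleep efficiency are measured twice in the same 15 people but compared with independent-sample t-tests, and latency sessions are declared independent, so neither the 5% error rate nor 95% coverage is assured.

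*Protocol*

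**What the plan says.** Protocol 3 describes a single-group pretest-posttest study of fifteen healthcare professionals and states: "Pre- and post-intervention assessments include ISI and quantitative EEG recordings".

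For latency, Protocol 7 says: "Independent-sample t-tests are used to compare latency before and after two weeks of use", and then: "Each sleep session is treated as an independent observation to maximize statistical power". SAP 5.3 repeats the rule: "Each sleep session will be treated as an independent observation to maximize statistical power".

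For efficiency, Protocol 7 has: "Independent-sample t-tests comparing pre-intervention and post-intervention sleep efficiency". SAP 5.4 agrees: "Independent-sample t-tests will be used to compare sleep efficiency before and after BDAS intervention". Neither efficiency passage says that sessions are pooled; the fault shown there is the unpaired test alone.

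Both documents set two-tailed significance at p < 0.05. SAP 5.4 plans 95% confidence intervals for efficiency. SAP 5.3 names none for latency, but SAP 9 lists a mean difference with a 95% interval for results in general. By contrast, ISI is analysed with a paired test (SAP 5.1), and paired tests are allowed for sleep-stage proportions (SAP 5.5).

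**The concern.** An independent-sample t-test assumes that the two samples are unrelated and that observations within each are independent. Here the same people appear on both sides, so the first assumption fails whenever pre and post values correlate. If a person contributes several latency sessions to a period, the second fails as well.

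The two failures pull in opposite directions. Ignoring positive pre-post correlation makes the standard error too large, so a real change can be missed. Treating repeated sessions as new people can make it too small, so chance differences are called significant. Which one dominates depends on how many recordings form each period. The documents do not say: the protocol speaks of pre- and post-intervention recordings, SAP 5.3 of initial use and after two weeks, and both of each session. A reader of the final p-value could not tell whether it was too strict or too lenient.

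These are the only objective endpoints with firmly planned significance tests. Onset success is descriptive (SAP 5.2), and stage proportions are tested only where appropriate (SAP 5.5). In an uncontrolled study with a self-reported primary outcome, readers will lean on them.

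**Working it through.** **The plan's own figures.** None is given for latency or efficiency; SAP 7 says no power calculation applies to secondary outcomes. The only figures concern ISI: reduction about 5, SD about 4, n = 15. Reading 4 as the SD of change, the standardised change is 5/4 = 1.25, the noncentrality is 1.25 × √15 = 4.84 on 14 df, and paired-t power is 99.4%. The claim of sufficient power for the primary analysis is supported. It says nothing about the two endpoints at issue.

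**Inputs.** From the documents: 15 participants, two-sided 5% level, independent-sample t-test, latency sessions as units. Assumed, because the documents are silent: normal data, total variance 1, split into shares for participant (a), participant-by-period (b) and residual (e), and the number of sessions per period (m). The results are ranges, not estimates for this trial.

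**Formula, equal session counts.** The true variance of the difference in means is 2(b + e/m)/15. The unpaired test on pooled sessions takes it to be about 2/(15m). The ratio of true to assumed variance is therefore about m·b + e. Below 1 the test is conservative; above 1 it is anti-conservative.

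**One recording per period (both endpoints).** With m = 1 the ratio is 1 − r, where r is the pre-post correlation. By simulation:

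| r | Type I error, unpaired | Power for 0.8 SD: unpaired | Paired |
|---|---|---|---|
| 0 | about 5% | 56% | 53% |
| 0.1 | 4.0% | 57% | 58% |
| 0.3 | 2.1% | 57% | 68% |
| 0.5 | 0.8% | 59% | 82% |
| 0.7 | 0.1% | 61% | 96% |

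At r = 0.5 the 95% interval half-widths are t(28)·√(2/15) = 0.748 unpaired and t(14)·√(1/15) = 0.554 paired, a ratio of 1.35.

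**Several pooled sessions, equal counts (latency only).** For shares 0.3/0.2/0.5 the ratio is 0.2m + 0.5, that is 0.9, 1.1, 1.5 and 1.9 at m = 2, 3, 5 and 7. Simulated type I error:

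| Shares a/b/e | m = 2 | 3 | 5 | 7 |
|---|---|---|---|---|
| 0.4/0.1/0.5 | 2.3% | 3.4% | 5.6% | 8.1% |
| 0.3/0.2/0.5 | 4.2% | 6.7% | 11.5% | 16.4% |
| 0.3/0.3/0.4 | 5.5% | 9.3% | 16.4% | 22.6% |

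Interval coverage is 100% minus these values; for 0.3/0.2/0.5 at m = 5 it is 88.5%. With b = 0, type I error stays below 5% (0.7% to 4.1% for participant shares 0.5 down to 0.1).

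**Unequal counts per participant and period.** Rounded type I error for shares 0.3/0.2/0.5, 0.4/0.1/0.5 and 0.5/0/0.5:
- 1 to 3 sessions: 6%, 4%, 2%.
- 1 to 7 sessions: 15%, 10%, 5%.
- 5 to 7 sessions: 14%, 8%, 1%.
- Either 1 or 7 sessions, 0.5/0/0.5: 13%.
- One initial session against 13 later ones for everyone: 4% (0.3/0.2/0.5) and 1% (0.5/0/0.5).

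**The stated reason, power.** With one recording per period there is nothing to pool, and the unpaired test loses power once r exceeds about 0.1. With five sessions, shares 0.3/0.2/0.5 and a 0.5 SD change, the pooled test rejects in 82% of trials against 64% for the paired test, but at a type I error of 11.5% against 5.0%. That gain is false precision.

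**Paired test on participant means.** Type I error stayed within about 4.3% to 5.3% in all settings.

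**The case against.** The strongest reply is that no correlation, variance share or session count is in the documents, so the size of the error is speculative. Inflation with equal counts needs both several sessions per period and participants who differ in their change; at two sessions it is absent in two of the three splits shown. Seven sessions per period would start the later period at night 8 of 14, which sits badly with a comparison after two weeks. Unequal counts alone, without participant-by-period variance, clearly inflate the error only in the artificial 1-or-7 pattern. All of this stands. It is why the conclusion is that the error rate is not assured, and not that it is inflated.

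A second reply is that SAP 7 calls the study exploratory and that the primary analysis is sound. That limits the consequence but does not make the tests valid, and the plan still attaches p < 0.05 and intervals to them. Their rank is also not uniform: Protocol 2 and SAP 1.3 make latency and efficiency secondary, while Protocol 6 lists the objective outcomes under its primary-outcome heading.

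Third, the simulations use normal data, whereas latency is non-negative and efficiency is bounded, so the near-5% level of the paired test is not shown for strongly skewed data. That is a reason to carry over the signed-rank fallback of SAP 5.1, not to keep the unpaired test. Finally, the sensitivity analyses in SAP 4 and 8 (complete cases, outliers, non-parametric alternatives, per-protocol set) are not stated to restore pairing or to account for repeated sessions.

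**Conclusion.** The concern holds. The independent-sample test is the wrong analysis for both endpoints because the same participants form both samples, and the independence of latency sessions is asserted for power without support. For efficiency, with one recording per period and positive correlation, the likely fault is a conservative test and intervals that are too wide. For latency the direction cannot be determined from the documents: across the settings shown, type I error runs from 0.1% to 22.6%. Those figures rest on normal data and assumed variance shares and session counts; that the design is paired rests on the documents alone. The ISI analysis is not affected. The wording should be changed before the analysis is run.

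**What to change.** In Protocol 7 and SAP 5.3 and 5.4:

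1. Remove the independent-sample t-tests and the statement that each session is an independent observation.
2. State how many recordings, and which, form each period. Say whether the protocol's pre-intervention recording and the SAP's initial use are the same recordings, for latency and for efficiency.
3. Average each participant's sessions within each period and apply a paired t-test, with the Wilcoxon signed-rank test if normality fails, as in SAP 5.1. Take the mean difference and 95% interval from the within-person differences, and name the standardiser for Cohen's d and Hedges' g. Say that this weights participants equally, where pooling weights sessions.
4. State in advance how latency is handled when sleep does not occur. SAP 5.2 says: "Sleep onset success will be defined as transition from wakefulness to any sleep stage during the recording period". A session that fails this has no latency under SAP 5.3, and SAP 4 rules out imputation. Averaging must not drop such sessions silently; at the least, report their number in each period.
5. Optionally, if there are two or more sessions per period, add a linear mixed model with a fixed period effect, random participant and participant-by-period effects, and small-sample degrees of freedom.

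The cost is wording in two documents and no new data. The number of observations falls from sessions to at most 15 participants with recordings in both periods, and the latency p-value may become less favourable.
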